#### **7.5.5.4 Population PK analysis**

All SOBI003 serum concentration data will be included in the population PK analysis. The objective is to explore the PK and the impact of covariates (e.g. body weight, age and dose level) on the PK of SOBI003.

#### **7.5.5.5 Population PK/PD analysis**

SOBI003 serum concentration data and SOBI003 CSF concentration data are planned to be included in the population PK/PD analysis. The objective of this analysis is to explore the relationship between SOBI003 exposure and selected biomarkers e.g. HS in serum and CSF.

## **7.5.6 Pharmacodynamic assessments**

### **7.5.6.1 Heparan sulfate**

Serum and urine are collected pre-infusion at Weeks 38, 52, 78 and 104 for analyses of HS. The blood sampling volume is a 0.3 mL at each sampling occasion.

CSF samples (200 µL) are collected at Weeks 52 and 104 for analyses of HS.

The serum and CSF HS analyses are performed at a central laboratory (York Bioanalytical Solutions Limited, [name]). Urine HS analysis is performed at another laboratory (Greenwood Genetic Center, [name]).

HS storage in serum and CSF is assessed using liquid chromatography tandem mass spectrometry (LC-MS/MS). The HS polymer itself is highly heterogeneous and therefore it is not possible to analyze at the intact molecule level. Therefore, the total level of HS is measured by analyzing selected disaccharides derived from enzymatic digestion (adaptation of method described in [Naimy et al. 2016](#)) (20).

Sampling, storage and shipment details are provided separately in the Study laboratory manual.

### **7.5.6.2 Future bioanalytical research**

As local regulations permit and provided that additional separate caregiver consent is given, blood (2 mL) and CSF (1 mL) samples are collected for future biomarker analyses at Weeks 52 and 104.

The samples will be stored at a central laboratory (York Bioanalytical Solutions Limited) for a maximum of 10 years following study completion (i.e. last patient's last visit in this study).

MPS IIIA is a very rare and severe disease for which there is a lot of research ongoing to further increase the understanding of disease pathology as well as diagnosis. The purpose of the sample storage is to allow future exploration/confirmation of new research findings. This includes:

- Biomarkers in serum and/or CSF with possible relation to the safety, tolerability, immunogenicity, PK and PD of SOBI003

The results of any such analyses will not be included in the Clinical Study Report for this study, but reported separately when analyzed, thus enabling exploration of any emerging novel disease-related discoveries of e.g., previously unknown disease alleles, inflammatory cytokines (e.g., IL1Ra, TNFα, calprotectin, neopterin), other HS biomarkers (e.g. HS metabolites), components of the complement system, and neurodegeneration (e.g., T-tau, hepatocyte growth factor, calbindin D).

Sampling details are provided separately in the Study laboratory manual.

### **7.5.6.3 Appropriateness of measurements**

Storage of HS in brain lysosomes causes pathological changes such as neuroinflammation and inhibition of autophagy in the MPS IIIA mouse model (21). As demonstrated in nonclinical studies, SOBI003 treatment reduces blood and brain HS levels, has favorable effects on

pathophysiological parameters such as neuroinflammation and lysosomal size and shows trends towards normalization of behavior in mice. Furthermore, the levels of HS derivatives in brain homogenate and CSF are strongly correlated, and the HS reduction at different dose levels of SOBI003 is paralleled in these two compartments.

Patients with MPS IIIA have elevated CSF HS levels in CSF as compared to healthy individuals (22). Also in humans, a reduction of HS in CSF is expected to mirror the reduction in brain and thus be a useful PD tool for dose selection.

## **8 Quality control and quality assurance**

This study will be conducted in compliance with this protocol, study specific procedures, INC Research SOPs, the ICH Guideline for Good Clinical Practice, and applicable regulatory requirements.

Monitoring visits to the study site are performed periodically during the study, to help ensure compliance with the protocol, study specific procedures and applicable regulatory requirements. Source documents are reviewed for verification of agreement with data in CRFs. All patient informed consent forms are reviewed. The investigator or institution guarantees access to source documents by Sobi, its representatives, and appropriate regulatory agencies.

The study site may be subject to a quality assurance audit by Sobi or its representatives, as well as inspection by appropriate regulatory agencies.

It is important that the investigator(s) and the(ir) relevant personnel are available during the monitoring visits and possible audits and that sufficient time is devoted to the process.

## **9 Statistical plan**

### **9.1 Determination of sample size**

All patients completing the FIH study ([SOBI003-001](#)) will be offered to continue into this extension study and the number of patients in the extension study is thus not based on statistical grounds.

However, the 14 patients in the NH study that will be used as an external control group had a mean baseline DQ of 58.9 points and declined with a mean of 30.4 (SD=12.1) DQ points during 24 months. Therefore, assuming very high likelihood of showing significant decrease in HS (with baseline mean of 5.2, std 1.8, correlation of 0.1 and a decrease of 80% the power is 99%), with 9 patients treated with SOBI003, the power to demonstrate an improvement in cognitive function is at least 80% if the decline is 9.8 DQ points for patients treated with SOBI003 as compared to a decline of 30.4 DQ points for untreated control patients (SD=13.0) and the reduction is homogeneous across age.

### **9.2 Definition of study populations**

The following analysis sets will be used in the statistical analyses.

Safety analysis set (SAF): The SAF will consist of all patients who received at least 1 dose of IMP.

The full-analysis set (FAS) is the efficacy analysis set which will consist of all patients enrolled in this extension study, and all patients in the NH study with a rapid progressive disease having a baseline age of 12-72 months (in the DQ analyses).

PK analysis set (PK): The PK set will consist of all patients where at least one SOBI003 dose has been administered correctly and where SOBI003 serum or CSF concentration data is available without any protocol deviation interfering with these results.

Immunogenicity analysis set (IAS): The IAS will consist of those subjects in the safety analysis set who have sufficient blood samples taken for ADA testing at baseline (screening visit) and at least one post-dose time-point

The SAF is used for the safety analysis, the FAS is used for the secondary and explorative efficacy variables.

A subpopulation of the FAS patients who are up to 30 months of age and in the FIH (SOBI003-001) study was initially assigned a dose at least as high as the dose selected for a planned phase III study will be included in future primary analysis population for demonstrating efficacy using combined data from the FIH study and the extension study, the Phase III trial and the corresponding patients in the NH study (control patients), consisting of the 14 patients with a rapid progressive MPS IIIA disease and a baseline age of 12 to 72 months.

### 9.3 Estimands

There will be a de facto estimand in the study, which is the primary estimand for the evaluation of efficacy. The estimand is the change in

- cognitive decline in all the patients from the population captured by the inclusion and exclusion criteria (see Sections 4.2.1 and Section 4.2.2) and the part of the NH population with a rapid progressive disease having a baseline age of 12-72 months, irrespectively of other medications used and adherence to treatment, and estimated by a repeated measures model of the change from baseline in DQ as described in Section 14.1.
- decline in HS levels in CSF in all the patients from the population captured by the inclusion and exclusion criteria (see Sections 4.2.1 and Section 4.2.2) irrespectively of other medications used and adherence to treatment, and estimated by a repeated measures model of the change from baseline in HS as described in Section 14.1.

To address foreseeable inter-current events, such as drop-outs, all missing values will be imputed (see Section 9.4.4) in accordance with the treatment policy principle. A sensitivity analysis will be performed where no imputations are performed, but all values are used: If a patient has a missing value in any assessment, then the same patient's non-missing scores will be used in the repeated measures model. The repeated measures model (see Section 9.4.4) handles missing values based on the missing at random (MAR) assumption. One further sensitivity analysis for DQ will address this assumption based on zero imputations, the rationale being that the patients not assessed are those expected to have a severe DQ decline. Other sensitivity analyses for this purpose will be tipping point analyses.

## **9.4 Overall statistical and analytical plan**

### **9.4.1 General statistical issues**

A detailed description of the statistical analyses to be performed will be documented in a statistical analysis plan to be completed prior to database lock.

### **9.4.2 Demographics and baseline characteristics**

Demographic and other baseline characteristics are listed and summarized with descriptive statistics.

### **9.4.3 Analysis related to primary objective**

Safety tabulations of AE data, vital signs data, and laboratory data are performed. Continuous variables are summarized using the number of patients, the mean, the standard deviation, the median, the minimum value, and the maximum value. Categorical variables are summarized using frequency counts and percentages.

### **9.4.4 Analysis related to secondary objectives**

#### **9.4.4.1 Key secondary endpoints at Week 104**

The first key efficacy endpoint related to the first key secondary objective is the change from baseline in Development Quotient (DQ) of neurocognitive development at Week 104 after start of SOBI003 treatment in the FIH study (SOBI003-001). Since this is a single-arm study without an internal control group, efficacy relating to neurocognition will be evaluated through a comparison to an external historical control group consisting of the available natural history data within the target study population, i.e. 14 patients with a rapid progressive disease and a baseline age of 12 to 72 months followed for 24 months (22).

The Bayley Scales of Infant and Toddler Development, Third Edition (BSID-III) or the Kaufman Assessment Battery for Children, Second Edition (KABC-II) will be used to assess neurodevelopment using the same approach as in the NH study (22). For each patient, an age-equivalent score (AEq) is determined using published normative data for the US population. An AEq score is the average score for a particular age. The Development Quotient is calculated as the AEq divided by the chronological age of the child multiplied with 100, i.e.  $DQ = 100 * AEq / Age$ .

For patients completing an assessment of both BSID-III and KABC-II, the BSID-III score will be used as a basis for calculating the DQ of neurocognitive development at baseline. A calibration of overlapping AEq scores between BSID-III and KABC-II will be done to assess if a patient outgrows the BSID-III test during the duration of the study. If confirmed, assessments of KABC-II will form the basis for calculating DQ of neurocognitive development for remaining study assessments.

DQ of neurocognitive development will be evaluated using a repeated measures analysis with the DQ measurements at baseline, Week 52, and Week 104 as response, and visit and visit-

treatment interaction as fixed factors, baseline age as covariate and an unstructured covariance matrix will be used to estimate the covariance pattern. The primary efficacy analysis set will thus consist of all patients included in this extension study (patients treated with SOBI003) and 14 patients from the NH study (untreated patients). The null hypothesis of no treatment effect will be tested with a significance test for the treatment\*time-effect, in the second step of the multiple testing procedure (see Section 9.4.5) The difference between 104 weeks and baseline will be used as the contrast of interest for the test.

All missing DQ values will be imputed. For a patient who stops treatment, let  $tp$  denote the turning point, i.e. the time point when the patient stops treatment. The patient's assessments as well as the time points for prediction are classified as being on either side of the turning point or at the turning point: prior to  $tp$ , at  $tp$ , or after  $tp$ . For patients who does not stop treatment, let  $tp = \infty$ , i.e. every time point is considered as prior to the  $tp$ . Let  $v$  denote a missing value to be imputed for a patient. The imputations will be based on two categories of predictions.

1) If the patient has two or more observations on the same side of  $tp$  as  $v$  (including a possible observation at  $tp$ ), then  $v$  is considered as *exclusively patient-predictable* ( $p_1$ ), i.e. it can be predicted by simple linear regression based only on the patient's data (intra -or extra-polation). On the other hand, if only one or zero observations exists on the same side of  $tp$  (from the particular patient) as  $v$  (including a possible observation at  $tp$ ), then it is considered as *non-predictable exclusively* from the patient's data.

2) The other type of prediction ( $p_2$ ), will be calculated by the use of a population derived slope, estimated based on the repeated measures model in Section 9.4.4 (without imputations), and a patient observation. There will be two cases; If the patient has one or more observations on the same side of  $tp$  as  $v$  (including a possible observation at  $tp$ ), then the nearest observation will be used together with a slope, which is based on the population (treated or untreated) of the same status as the side of  $tp$  where the prediction time point is situated, as well as the interval relative the visits which contain the prediction time point. The other case is when there is no observation on the same side of  $tp$  as  $v$  (and no observation at  $tp$ ). In this case, a prediction at  $tp$  will first be calculated, based on the same method as described above (under 2) but on the other side of  $tp$ , i.e. the nearest observation relative  $tp$  on the other side of  $tp$  will be used together with a slope based on the population (treated or untreated) of the same status as the side of  $tp$  where this nearest observation time point is situated, as well as the interval relative the visits which contain the  $tp$ . This prediction at the  $tp$  is in then used to predict  $v$  as described under the first case (under 2).

For each missing value  $v$ , the following algorithm is used to impute  $v$  by  $i$ :

If  $p_1$  does not exists, then  $p_2$  is used, i.e.,  $i = p_2$ .

Otherwise, a weighted average will be used for the imputation:  $i = w_1 p_1 + w_2 p_2$ , where  $w_1 = \exp(-\lambda \ln(2)/3)$  and  $w_2 = 1 - \exp(-\lambda \ln(2)/3)$  and  $\lambda$  is the distance in months between the time point for prediction and the nearest available non-missing patient assessment time point. The exponential function is motivated by an exponential decrease of relevance of individual patient data relative to population data with increasing time, and the coefficient  $\ln(2)/3$  is chosen such that population data reach the same weight as individual patient data after 75 % of the distance between 2 visits, i.e. 3 months. When individual patient data is available near a missed visit, the patient data weight is near 100 %, and when the distance is near one year on the other hand, the individual patient data weight has decreased to nearly 6 %.

The second key efficacy endpoint related to the second key secondary objective is the change from baseline in HS levels in CSF at Week 104 after start of SOBI003 treatment in the FIH study (SOBI003-001).

For the purpose of the multiple testing procedure (see Section 14.3), the linear repeated measures analysis with untransformed HS levels in CSF will be used, identical to the DQ analysis with the exception of the treatment factors.

The time effect is used to judge the HS level change in CSF. The null hypothesis of no change will be tested with a significance test for the time-effect in the first step of the multiple testing procedure (see Section 9.4.5). The difference between 104 weeks and baseline will be used as the contrast of interest for the test. Missing HS values will be imputed according to the same methodology as for the missing DQ values.

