Statistical methods:	
Safety tabulations of AE data and laboratory data are performed. Continuous variables are summarized using the number of patients, the mean, the standard deviation, the median, the minimum value, and the maximum value. Categorical variables are summarized using frequency counts and percentages.
 
Change from baseline in DQ of neurocognitive development at Week 104 and change from baseline in CSF HS at Week 104 will be evaluated jointly in a hierarchical approach.
 
DQ of neurocognitive development will be evaluated using a repeated measures analysis with the DQ measurements at the individual time points as response, and visit and visit-treatment interaction as fixed factors, baseline age as covariate and an unstructured covariance matrix will be used to estimate the covariance pattern. The control is an untreated group of MPS IIIa patients from a NH trial. The null hypothesis of no treatment effect will be tested with a significance test for the treatment*time-effect in the second step of the multiple testing procedure. The difference between 104 weeks and baseline will be used as the contrast of interest for the test.
 
To assess the PD effect of SOBI003 on HS levels in CSF, serum and urine, linear models are used to model the change from baseline in HS levels as dependent variable, for both logged HS levels and untransformed HS levels, and baseline level and age as continuous covariates, and accumulated dose as covariate and sex as factor. The analyses are conducted for each assessment time point. In addition, linear analyses with HS levels, both logged HS levels and untransformed HS levels, in CSF, serum and urine, as dependent variable, and baseline level and age as continuous covariates, and accumulated dose as covariate and sex as factor will be performed across all assessments, with

assessment as a repeated factor.

For the purpose of the multiple testing procedure, the linear repeated measures analysis with untransformed HS levels will be used, identical to the DQ analysis with the exception of the treatment factors.

The time effect is used to judge the HS level change in CSF. The null hypothesis of no change will be tested with a significance test for the time-effect in the first step of the multiple testing procedure. The difference between 104 weeks and baseline will be used as the contrast of interest for the test. PK results are presented by dose level using descriptive statistics.

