#### **9.4.5 Multiple comparison procedure**

A hierarchical approach will be used for the key secondary co-endpoints.

The primary analysis will be based on a 2-sided test using a significance level of 0.05. A stepwise sequential testing procedure will be used to ensure a multiple level of significance of 0.05.

- 1st step: The null hypothesis of no difference between the treatments with respect to the reduction from baseline HS in CSF at 24 months will be tested using a significance level of 0.05. If the null hypothesis is rejected, then it will be concluded that SOBI003 reduces HS. Furthermore, the 2nd step of the sequential testing procedure will be performed.
- 2nd step: The null hypothesis of no difference between the treatments with respect to the change in DQ score at 24 months will be tested using a significance level of 0.05. If the null hypothesis is rejected, it will be concluded that SOBI003 improves cognitive function as compared to untreated patients.

This multiple comparison procedure controls that the multiple level of significance is no more than 5%.

Formally, the second confirmatory step will only be valid after the 1st step has been successfully met.

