14.1 The DQ endpoint

One of the key secondary objectives is to assess the effect of SOBI003 on neurocognition, as compared to untreated MPS IIIA patients from a NH control. The key endpoint related to this

objective is the change from baseline in DQ of neurocognitive development at 104 weeks of treatment, and will be estimated by a model based contrast.

To address the efficacy objective, a repeated measure analysis will be utilized where DQ is the response variable and time, baseline age, time*baseline age and treatment*time are fixed effects and the dependency between observations within the same patient is represented by an unstructured variance-covariance matrix.

The time window is two weeks, i.e., if the assessment is more than two weeks too early or more than two weeks too late, then the DQ is set to missing for that assessment.

In the NH study, a simple linear regression model was used, i.e. with DQ as the response variable and the age of the child as dependent variable (Shapiro et al 2016). As the aim in this clinical development program is to demonstrate that treatment with SOBI003 is efficacious and the effect of treatment is dependent on the time the patient has been treated, this model needs to be adopted so that time and baseline age are factors rather than the actual age of the child (which is the sum of the baseline age and the time in study). The results from the NH study suggest that the decline in DQ is not linear across all ages, and an interaction term time*baseline age is planned to be included in the model to allow for such a non-linearity. Also an unstructured variance-covariance matrix is planned to be used to account for the dependency between observations within the same patient. As a further justification for the model, it should be noted that time, baseline age and time*baseline age are all significant factors in the NH study.

To represent the treatment effect without constraint to a specific relation across visits, a term treatment*time is planned to be included in the model. This effect is used to judge the treatment effect. The null hypothesis of no treatment effect will be tested with a significance test for the treatment*time-effect in the second step of the multiple testing procedure (see Section 14.3). The difference between 104 weeks and baseline will be used as the contrast of interest for the test.

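### The protocol and SAP give different confirmatory DQ models: only the SAP's, with time by baseline age, adjusts the Week 104 contrast for age, and nothing says which prevails

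*Protocol*

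**What the plan says.** Protocol 9.4.4.1 sets out a repeated measures model with the "DQ measurements at baseline, Week 52, and Week 104 as response, and visit and visit"-by-"treatment interaction as fixed factors, baseline age as covariate and an unstructured covariance matrix will be used to estimate the covariance pattern". The synopsis (Statistical methods) has the same list: "visit and visit-treatment interaction as fixed factors, baseline age as covariate and an unstructured covariance matrix". Neither contains an age-by-visit term.

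SAP 14.1 states that "time, baseline age, time*baseline age and treatment*time are fixed effects". It argues that decline is not linear over all ages and adds that "time, baseline age and time*baseline age are all significant factors in the NH study".

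Both documents test the same quantity: "The difference between 104 weeks and baseline will be used as the contrast of interest for the test". It is step 2 of the formal hierarchy (Protocol 9.4.5, SAP 14.3), for which "The primary analysis will be based on a 2-sided test using a significance level of 0.05". Both documents impute all missing DQ values in the main analysis.

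**The concern.** The treated children are compared with 14 NH children aged 12 to 72 months at baseline, without randomisation. If the 2-year change in DQ depends on age, as the SAP reports for the NH data, any difference in mean age between the groups enters the treatment effect unless the model removes it. The protocol lists baseline age as a covariate, so it appears to adjust for age. Whether it adjusts the quantity actually tested depends on a term that only the SAP contains.

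The discrepancy spreads. The imputation slopes are estimated from the repeated measures model of each document. The HS analysis for step 1 is defined as the DQ model without its treatment factors, so it inherits whichever version is used. The SAP (Section 17) also plans the same methods for the pivotal Phase III analysis.

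**Working it through.** **The plan's own figure.** Inputs from Protocol 9.1 and SAP 7.1: 9 treated, 14 NH, declines of 9.8 and 30.4 DQ points (difference 30.4 − 9.8 = 20.6), SD 13.0. Taken as an unadjusted two-group comparison of change, SE = 13.0 × √(1/14 + 1/9) = 5.55. Two-sided power at 0.05 is 94.2% (noncentral t, 21 df) or 96.0% (normal). The stated bound of at least 80% is met, and the point below does not depend on it.

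**Algebra.** Let T be treatment, a baseline age and v visit.

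- Protocol: mean DQ = μ_v + τ_v·T + β·a. Week 104 minus baseline is (μ_104 − μ_0) + (τ_104 − τ_0)·T. The term β·a has gone. With complete data each estimated τ_v is the raw group difference at that visit minus the same multiple of the age difference. The contrast is therefore exactly the raw difference in mean change.
- SAP: mean DQ = μ_v + τ_v·T + β_v·a. The change keeps (β_104 − β_0)·a, so the contrast is the age-adjusted difference in change.

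**Numerical check.** REML fits (three visits, unstructured covariance) to three simulated datasets with 14 NH and 9 treated patients and no drug effect. Assumed inputs were an age slope of 0.5 points per month and mean ages of 45 and 30 months.

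| Dataset | Raw difference in change | Protocol model (SE) | SAP model (SE) | Regression of change on treatment and age |
|---|---|---|---|---|
| 1 | 2.739 | 2.739 (6.01) | −5.617 (10.11) | −5.617 |
| 2 | 6.086 | 6.086 (5.32) | 5.371 (7.06) | 5.371 |
| 3 | 3.560 | 3.560 (3.96) | −0.360 (4.08) | −0.360 |

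The protocol model reproduces the raw difference, and the SAP model reproduces the age-adjusted one. With missing values left unimputed, as in the sensitivity analysis, the cancellation is only approximate: in dataset 1 with three values removed, the protocol model gave 2.86 against 1.65 for raw complete cases.

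**Size.** Bias = (age slope of the 2-year change) × (difference in mean baseline age). Neither factor is in the documents, so both are assumed. The error is the chance of p < 0.05 with no drug effect, from the noncentral t with 21 df, SE 5.55 and noncentrality bias/5.55.

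| Slope (points/month) | Gap (months) | Bias (points) | Two-sided error |
|---|---|---|---|
| any | 0 | 0 | 5.0% |
| 0.2 | 6 | 1.2 | 5.5% |
| 0.2 | 12 | 2.4 | 7.0% |
| 0.5 | 6 | 3.0 | 8.1% |
| 0.5 | 12 | 6.0 | 17.8% |

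Against the planned difference of 20.6, this is 1.2/20.6 = 6% to 6.0/20.6 = 29%.

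**Is such a slope plausible?** As an illustration only, take DQ = 100 × AEq/age, the NH mean baseline DQ of 58.9 at every age, and no gain in AEq over 24 months. The DQ loss is then 58.9 × 24/(age + 24): 29.5 points at 24 months, 23.6 at 36 and 19.6 at 48. The slopes are (29.5 − 23.6)/12 = 0.49 and (23.6 − 19.6)/12 = 0.33 points per month.

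**The case against.** The strongest reply is that the SAP model is clearly the intended one. Protocol 9.4.1 leaves the detailed description to the SAP. Protocol 9.3 says the DQ estimand is estimated as set out in Section 14.1, and 9.4.4.1 cites Section 14.3. Those are the SAP's numbers for the DQ model and the testing procedure; Section 14 of the protocol is the reference list. The SAP names one model, justifies it, and does not offer the protocol version even as a sensitivity analysis. Most of this stands. A reader might infer that the planned analysis ignores age, or that the sponsor has kept a free choice between two models. The documents do not support either: the harm arises only if the protocol wording is what gets run. But no passage gives the SAP precedence, Protocol 9.3 also cites its own Section 9.4.4, and the SAP does not flag the term as a change from the protocol. A complete list of fixed effects that omits the decisive term is also more than missing detail.

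The second reply is that the size is hypothetical. That stands too. Protocol 7.2 says comparable patients will be included and SAP 4.2 aims for a population close to the NH study, so the gap may be small. The extension's own criteria (Protocol 7.3) set no age limit, however, and 9 to 12 treated children cannot guarantee balance.

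Third, a reader might take the upper error rate as the risk of a false efficacy claim. It is not: the direction is unknown. In a simulation with slope 0.5 and a 12-month gap working against the drug (9 v 14, SD 12.1), the error was 14.2%, of which 13.8% was false harm and 0.4% false benefit. The mirror case gives about 14% false benefit.

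**Conclusion.** The two documents specify different formal tests for step 2, and the difference matters. With imputed, complete data the protocol model leaves the contrast unadjusted for age, while the SAP model adjusts it. The cancellation is exact and needs no assumption about the data.

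The consequence is conditional. It is nil if mean ages agree or if the SAP model is the one run. Otherwise, under the assumed slopes and gaps, the bias is roughly 1 to 6 DQ points in either direction, with a two-sided error of about 5.5% to 18%.

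A reader might also infer that the SAP model removes the bias altogether. That holds only if the change is linear in baseline age. With an assumed U-shaped age effect, linear adjustment left 0.7 points (12-month gap) to 2.4 points (20-month gap), against 1.9 and 4.9 unadjusted. It reduces the bias but may not remove it.

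**What to change.** Amend the synopsis and Protocol 9.4.4.1 to the SAP model (time, baseline age, time by baseline age, treatment by time, unstructured covariance). Record this as a change from the protocol, so that one confirmatory model stands in both documents and the imputation slopes follow from it.

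For step 1, state the age at which the HS time contrast is evaluated. In a one-group model with time by age, that contrast changes with the chosen age, and neither document names one; the mean baseline age of the treated patients would be one choice.

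The cost is protocol wording plus one parameter per post-baseline visit, already in the SAP. Adjustment costs some precision if ages differ. With a 12-month gap and an assumed within-group age SD of 12 or 18 months, the variance of the contrast rises by a factor of 1.24 or 1.11, and power for the planned 20.6 points is 88.7% or 91.8%, still above the stated 80%.
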